### 5.1.2 Justification of the Trial Design

[REDACTED] MET51 is a study that will be conducted as part of the Phase III of development of the MenACYW conjugate vaccine in which the vaccine would be evaluated in the age group 12 to 23 months of age. This age group has been selected since the rates of meningococcal disease are highest in young children with a secondary peak in adolescents and young adults aged 11 to 19 years (36).

This study is designed to evaluate the immunogenicity responses and safety profiles following the administration of a single dose of the MenACYW conjugate vaccine in toddlers 12 to 23 months of age who either are meningococcal naïve or have received monovalent MenC vaccination during infancy.

Data in toddlers who have previously received MenC during infancy are needed as part of the overall data required by the European Medicines Agency (EMA) in the context of achieving licensure with a broad age indication. These data will be complementary to the data generated in this study in meningococcal vaccine-naïve toddlers as well as in the MET54 study where MenC-naïve toddlers in the EU were randomized either to receive a single dose of MenACYW conjugate vaccine or Nimenrix®. The MET51 study collects data about the MenC conjugate vaccine administered to the study subjects during their first year of life (either TT protein as conjugate or CRM197 protein as conjugate); descriptive analysis is planned as a part of the observational objectives in this study to account for this difference in the background vaccination.

Since the primary objectives of this study have serological endpoints and the vaccines for the study groups have different appearances, the study has a modified double-blind design. This means it contains an unblinded vaccine administrator while the rest of the study team, including laboratory technicians in charge of executing the serological testing, remain blinded to the subjects' group allocations throughout the entire study up to the database lock to avoid any bias.

The unblinded site personnel, who will not participate in any safety evaluation of the subjects during study conduct, will prepare all vaccines, and then administer the vaccines to the subjects.

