4.4.3.3 Duration of the Study

The duration of the study is computed as follows:

Maximum of all subjects (date of last visit, date of termination) – Minimum of all subjects (date of Visit 1) + 1.

5 Statistical Methods and Determination of Sample Size

The statistical analyses will be performed under the responsibility of the Sponsor's Biostatistics platform using SAS[®] Version 9.4 software or later.

The results of the statistical analysis will be available in the final clinical study report. For descriptive purposes, the following statistics will be presented:

Table 5.1: Descriptive statistics produced

Baseline characteristics and follow-up description	Categorical data	Number of subjects. Percentage of subjects.
	Continuous data	Mean, standard deviation, quartiles, minimum, and maximum.
Clinical safety results	Categorical data	Solicited: Number and percentage (95% CIs) of subjects. Unsolicited: Number and percentage (95% CIs) of subjects, and number of events.
Immunogenicity results	Categorical data (seroresponse, ≥ 4 fold rise, cutoff)	Number and percentage (95% CIs) of subjects.
	Continuous data (titer / concentration)	Log ₁₀ : Mean and standard deviation. Anti-Log ₁₀ (work on Log ₁₀ distribution, and anti-Log ₁₀ applied): Geometric mean (GM), 95% CI of the GM. Graphical representation by Reverse Cumulative Distribution Curve (RCDC).

The confidence interval (CI) for the single proportion will be calculated using the exact binomial method (Clopper-Pearson method, quoted by Newcombe (1)). For immunogenicity results, assuming that Log₁₀ transformation of the titers follows a normal distribution, at first, the mean and the 95% CI will be calculated on Log₁₀ (titers) using the usual calculation for normal distribution (using Student's t distribution with n-1 degree of freedom), then antilog transformations will be applied to the results of calculations, in order to provide GMs and their 95% CI.

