5.1.1.2 Statistical Methods

5.1.1.2.1 Statistical Method for Co-primary Objective 1

Each of the serogroups A, C, Y, and W will be tested separately. If the lower limit of the 2-sided 95% confidence interval (CI) of the difference between the 2 percentages is $> -10\%$, the inferiority assumption will be rejected.

For the 4 non-inferiority hypotheses using the response rates (percentages of subjects who achieve an hSBA titer $\geq 1:8$), the 95% CI will be stratified on the priming status (meningococcal vaccine naïve or primed monovalent MenC vaccination during infancy) and calculated using the Wald method (normal approximation). Weighted average of the difference over strata will be calculated using the Minimal Risk weights with the null variance method (2).

The 100(1- α)% two-sided CIs for the difference in proportions between two groups using the Minimum Risk Weights with the null variance are calculated as follows:

$$\hat{\delta}_w \pm Z_{\alpha/2} \sqrt{\left\{ \sum_{i=1}^s w_i^2 \hat{V}_0(\hat{\delta}_i) \right\}}$$

where $i=1,2, s=2, \hat{\delta}_w = \sum_{i=1}^s w_i \hat{\delta}_i = \sum_{i=1}^s w_i (\hat{P}_{iB} - \hat{P}_{iA}), \hat{P}_{iA}, \hat{P}_{iB}$ are the observed response rates for MenACYW vaccine group and the Nimenrix[®] group respectively at stratum $i, Z_{\alpha/2}$ is the 100(1-

$\alpha/2$)th percentile of the standard normal distribution, and w_i are the weight assigned at stratum i , and

$\hat{V}_0(\hat{\delta}_i) = \frac{\tilde{P}_{iA}(1-\tilde{P}_{iA})}{n_{iA}} + \frac{\tilde{P}_{iB}(1-\tilde{P}_{iB})}{n_{iB}}$ is the null variance, where $\tilde{P}_{iA}, \tilde{P}_{iB}$ are the constrained maximum likelihood estimates (MLEs) of response rates of MenACYW and Nimenrix at stratum i , and n_{iA}, n_{iB} are the sample sizes for MenACYW and Nimenrix at each stratum.

The Minimum Risk method computes the weights w_i as follows:

$$w_i = \frac{\beta_i}{\sum_{k=1}^s V_k^{-1}} - \left(\frac{\alpha_i V_i^{-1}}{\sum_{k=1}^s V_k^{-1} + \sum_{k=1}^s \alpha_k \delta_k V_k^{-1}} \right) \left(\frac{\sum_{k=1}^s \delta_k \beta_k}{\sum_{k=1}^s V_k^{-1}} \right)$$

where $\alpha_i = \delta_i \sum_{k=1}^s V_k^{-1} - \sum_{k=1}^s \delta_k V_k^{-1}$ and $\beta_i = V_i^{-1} \left(1 + \alpha_i \sum_{k=1}^s f_k \delta_k \right)$, $V_i = V(\hat{\delta}_i)$, and f_i is the fraction of subjects in the target population that belong in stratum i ($\sum_{i=1}^s f_i = 1$).

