For two strata, with observed values for V_i, f_i , and δ_i the formula reduces to the following:

$$\hat{w}_1 = \frac{\hat{V}_2 + \hat{f}_1(\hat{\delta}_1 - \hat{\delta}_2)^2}{\hat{V}_1 + \hat{V}_2 + (\hat{\delta}_1 - \hat{\delta}_2)^2}, \quad \hat{w}_2 = 1 - \hat{w}_1.$$

The overall non-inferiority of this objective will be demonstrated if all 4 individual null hypotheses are rejected.

5.1.1.2.2 Statistical Method for Co-primary Objective 2

Each of the serogroups A, C, Y, and W will be tested separately. If the lower limit of the 2-sided 95% CI of the difference between the 2 percentages is $> -10\%$, the inferiority assumption will be rejected.

For the 4 non-inferiority hypotheses using the response rates (percentages of subjects who achieve an hSBA titer $\geq 1:8$), the CI of the difference in proportions will be computed using the Wilson Score method without continuity correction (3).

Let $\hat{\theta} = p_1 - p_2$, then $L = \hat{\theta} - \delta$ and $U = \hat{\theta} + \varepsilon$ are respectively the lower and the upper limits of the CI, where:

$$\delta = Z_{0.025} \sqrt{\left\{ \frac{l_1(1-l_1)}{n_1} + \frac{u_2(1-u_2)}{n_2} \right\}}$$

$$\varepsilon = Z_{0.025} \sqrt{\left\{ \frac{l_2(1-l_2)}{n_2} + \frac{u_1(1-u_1)}{n_1} \right\}}$$

l_1 and u_1 are calculated from the CI of the single proportion in Group 1 given by:

$$\frac{(2n_1p_1 + Z_{0.025}^2 \pm Z_{0.025} \sqrt{(Z_{0.025}^2 + 4n_1p_1(1-p_1))})}{2(n_1 + Z_{0.025}^2)}$$

l_2 and u_2 are calculated from the CI of the single proportion in Group 2 given by:

$$\frac{(2n_2p_2 + Z_{0.025}^2 \pm Z_{0.025} \sqrt{(Z_{0.025}^2 + 4n_2p_2(1-p_2))})}{2(n_2 + Z_{0.025}^2)}$$

where $Z_{0.025}$ is the upper 97.5th percentile of the standard normal distribution.

The overall non-inferiority of this objective will be demonstrated if all 4 individual null hypotheses are rejected.

To conclude, non-inferiority in toddlers who either are meningococcal vaccine-naïve or have received monovalent MenC vaccination during infancy and non-inferiority in meningococcal vaccine-naïve subjects have to be demonstrated.

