5.1.2 Hypotheses and Statistical Methods for Secondary Objectives

5.1.2.1 Hypotheses

No hypotheses will be tested. Descriptive statistics will be presented.

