5.1.2.2 Statistical Methods

5.1.2.2.1 Statistical Method for Secondary Objective 1

Thirty days after the administration of MenACYW conjugate vaccine or Nimenrix[®] in toddlers who either are meningococcal vaccine naïve or have received monovalent MenC vaccination during infancy, the hSBA geometric mean titer ratio (GMTR) between MenACYW conjugate vaccine or Nimenrix[®] will be calculated, and 95% CI will be provided. The 95% CI of the ratio of post-vaccination GMTs will be stratified on the priming vaccination status (meningococcal vaccine naïve or primed monovalent MenC vaccination) and calculated using an analysis of variance (ANOVA) model of log₁₀-transformed titers.

5.1.2.2.2 Statistical Method for Secondary Objective 2

Thirty days after the administration of MenACYW conjugate vaccine or Nimenrix[®] in meningococcal vaccine naïve toddlers, the hSBA GMTR between MenACYW conjugate vaccine or Nimenrix[®] will be calculated, and 95% CI will be provided.

5.1.2.2.3 Statistical Method for Secondary Objective 3

Thirty days after the administration of MenACYW conjugate vaccine or Nimenrix[®] in toddlers who received monovalent MenC vaccination during infancy, the hSBA GMTR between MenACYW conjugate vaccine or Nimenrix[®] will be calculated, and 95% CI will be provided.

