5.1.3.2 Statistical Methods

Immunogenicity

Descriptive statistics will be provided for the antibody titers against meningococcal serogroups contained in MenACYW conjugate vaccine and Nimenrix[®]. In general, categorical variables will be summarized and presented by frequency counts, percentages, and CIs. The 95% CIs of point estimates will be calculated using the normal approximation for quantitative data and the exact binomial distribution (Clopper-Pearson method) for percentages (1).

For GMTs, 95% CIs of point estimates will be calculated using normal approximation assuming they are log-normally distributed.

Reverse cumulative distribution curve (RCDC) figures will be provided for the antibody titers against meningococcal serogroups contained in MenACYW conjugate vaccine and Nimenrix[®] treatment groups.

In summary, descriptive analyses on A, C, Y, and W serogroups will include but not be limited to:

- hSBA GMT and 95% CI at D0 and D30
- hSBA titer distribution and RCDC
- Percentage of subjects with hSBA titer $\geq 1:4$ and $\geq 1:8$ and 95% CI at D0 and D30
- Percentage of subjects with hSBA titer ≥ 4 -fold rise from pre-vaccination to post-vaccination, and 95% CI

- hSBA vaccine seroresponse¹ rate and 95% CI
- rSBA² GMT and 95% CI at D0 and D30
- rSBA titer distribution and RCDC
- Percentage of subjects with rSBA titer \geq 4-fold rise from pre-vaccination to post-vaccination, and 95% CI
- rSBA vaccine seroresponse³ rate and 95% CI
- Percentage of subjects with rSBA titers \geq 1:8 and \geq 1:128 and 95% CI at D0 and D30

Safety

For this trial, the safety data will be assessed by applying descriptive statistical methods, supplemented by the calculation of CIs to aid interpretation. The exact binomial distribution (Clopper-Pearson method) for proportions will be used in the calculation of the 95% CIs of events.

The frequency and percentage of subjects who had solicited injection site reactions and solicited systemic reactions and their 95% CIs will be provided. These events will be tabulated by the type of reactions and intensity for each study group. These events will also be summarized by other categories specified in the endpoints (e.g. time of onset, number of days of occurrence, actions taken).

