5.1.4 Complementary outputs

Additional analyses by gender will be provided in Appendix 15 of the CSR.

Immunogenicity analyses:

- hSBA GMTs and 95% CI at each time point – Per-Protocol Analysis Set
- Vaccine seroresponse against meningococcal serogroups A, C, Y, and W measured by hSBA and 95% CI – Per-Protocol Analysis Set
- rSBA GMTs and 95% CI at each time point – Per-Protocol Analysis Set
- Vaccine seroresponse against meningococcal serogroups A, C, Y, and W measured by rSBA and 95% CI – Per-Protocol Analysis Set

Safety analyses:

Safety overview after vaccine injection –Safety Analysis Set

Some demographics tables will be also described by MenC primed background.

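### Does the plan need a Group 3 minus Group 4 difference in the percentage with hSBA ≥1:8 for MenC-primed toddlers?

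*SAP*

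**What the plan says.** **Co-primary objectives.** Co-primary 1 compares Groups 1 and 3 with Groups 2 and 4, stratified on priming status. SAP 5.1.1.2.1 states the estimand: "Weighted average of the difference over strata will be calculated using the Minimal Risk weights with the null variance method". Co-primary 2 compares Group 1 with Group 2, naïve toddlers only. The success rule in SAP 5.1.1.2.2 asks for a pass on each of the two, the combined population and the naïve stratum: "either are meningococcal vaccine-naïve or have received monovalent MenC vaccination during infancy and non-inferiority in meningococcal vaccine-naïve subjects have to be demonstrated".

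**Primed toddlers alone.** Secondary objective 3 (Protocol 2.2) compares GMTs, its endpoint (Protocol 9.2.1.1) is GMTs, and its method (Protocol 12.1.2.3, SAP 5.1.2.2.3) is the ratio: "in toddlers who received monovalent MenC vaccination during infancy, the hSBA GMTR between MenACYW conjugate vaccine or" Nimenrix, with a 95% CI. For all secondary objectives, SAP 5.1.2.1 says: "No hypotheses will be tested. Descriptive statistics will be presented".

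**Percentages.** SAP 5.1.3.2 lists the percentage with hSBA ≥1:8 at D0 and D30, with intervals from "the exact binomial distribution (Clopper-Pearson method) for percentages". SAP Table 5.1 gives the row "Categorical data (seroresponse, ≥ 4 fold rise, cutoff") as number and percentage with 95% CI. The observational objectives (SAP 2.3) describe responses to each vaccine in MenC-TT-primed and MenC-CRM-primed toddlers. The list in SAP 5.1.3.2 is expressly open-ended. SAP 5.1.4 adds sex-specific tables ("Additional analyses by gender will be provided in Appendix 15 of the CSR") but no difference for primed toddlers.

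**The concern.** Protocol 5.1.2 gives the primed stratum weight of its own: "Data in toddlers who have previously received MenC during infancy are needed as part of the overall data required by" the European regulator. These toddlers are randomised separately, 204 v 102. Co-primary 2 leaves them out, and co-primary 1 gives them about one third of the weight. Good results in naïve toddlers can therefore offset a poor result in primed toddlers.

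The endpoint that carries the -10% margin is the share reaching 1:8. For primed toddlers alone, the only listed contrast between vaccines is on mean log titer. Two single-group intervals do not give an interval for a difference. If a pooled success were read as covering each subgroup, a primed deficit beyond the margin could sit behind a positive trial with no pre-specified interval to describe it.

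**Working it through.** The plan's expected response rates and power tables are blacked out in both documents, so there is no stated figure to reproduce. All rates below are assumptions. Group sizes are the planned ones (306, 306, 204, 102), differences are MenACYW minus Nimenrix as in the hypotheses, and figures are for one serogroup.

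**1. Can both co-primaries pass with a large primed deficit?** Take naïve 297/306 v 297/306 and primed 159/204 v 99/102.

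- Differences: naïve 0; primed 0.7794 - 0.9706 = -0.1912.
- Sample variances: V1 = 0.000187, V2 = 0.001123. Squared gap between strata 0.03655; f1 = 612/918 = 0.6667.
- Weight (SAP two-strata formula): w1 = (0.001123 + 0.6667 × 0.03655) / (0.000187 + 0.001123 + 0.03655) = 0.673, so the primed weight is 0.327.
- Weighted difference: 0.327 × (-19.12) = -6.25 points.
- Null variances with the constraint at -10%: 0.000387 and 0.001375. SE = √(0.673² × 0.000387 + 0.327² × 0.001375) = 0.01795.
- Co-primary 1 lower limit: -6.25 - 1.96 × 1.795 = **-9.8%**. SAP 5.1.1.2.1 does not state the constraint value; at 0 the limit is -9.6%. Pass either way.
- Co-primary 2 (Wilson score, SAP 5.1.1.2.2): 0 - 1.96 × √(0.9451 × 0.0549/306 + 0.9845 × 0.0155/306) = **-2.9%**. Pass.
- Primed only, same Wilson-score formula: **-19.1% (95% CI -25.6% to -11.7%)**.

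So the arithmetic behind the concern is right.

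**2. Would the planned outputs hide it?** The exact single-group intervals in this example are 71.6–83.4% (159/204) and 91.6–99.4% (99/102). They do not overlap.

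**3. How does that hold up in simulation?** Assumptions: 275/275/184/92 evaluable (about 10% excluded), no naïve difference, one serogroup, true primed deficits of 12/15/18/20 points, null constraint at -10%.

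| Assumed rates | Both co-primaries pass | Both pass and whole primed CI below -10% |
|---|---|---|
| (a) naïve 97%, primed Nimenrix 97% | 97/86/62/43% | 4/12/20/19% |
| (b) naïve 90%, primed Nimenrix 90% | 75/58/39/28% | 1/2/4/4% |
| (c) naïve 90%, primed Nimenrix 97% | 82/64/43/30% | 2/8/13/14% |

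In every simulated trial counted in the last column, the planned exact intervals for the two primed arms did not overlap. With a true deficit of 15 points and both co-primaries passed, a CI for the difference would lie wholly below 0 in about 98% of trials in (a) and 79% in (b). The planned intervals fail to overlap in about 85% and 40%.

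**4. Does the pattern depend on the naïve result?** Yes. At full planned numbers, an 80% control rate and a naïve deficit of 2 points, the largest primed deficit that still passes both is 9.8 points, which is under the margin.

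**5. What would the added interval show if the vaccines were equal?** At 184 v 92, the chance that the primed lower limit is at or below -10% is 0.190 per serogroup at 90% responders. Over four serogroups, taken as independent, 1 - (1 - 0.190)⁴ = 0.57. At 97% responders the per-serogroup chance is 0.004 and the four-serogroup figure is about 1.5%.

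**6. Does any stated claim lack its analysis?** Set side by side: the combined-population claim has the stratified interval; the naïve claim has the Wilson-score interval; the primed GMT objective has the GMT ratio and CI; the descriptive objectives have percentages, exact CIs and titer distributions. No claim is left over.

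**The case for a change.** The strongest case for the addition is this. A difference chosen after unblinding carries less weight than one named beforehand, and the open-ended list permits it without committing to it. Readers who compute it themselves may use different interval methods. The GMT ratio is no substitute, because it does not measure the share below 1:8. The phase II comparison with Nimenrix (Protocol 1.2.2.2) enrolled naïve toddlers only. The row would cost no subjects, samples or alpha.

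Most of that is true, and it shows the row could be useful. In scenario (b) an interval for the difference detects a 15-point deficit clearly more often than non-overlap of the single-group intervals does (79% v 40%). But it does not show that the plan is wrong. Table 5.1 commits to numbers as well as percentages, so the difference and a Wilson-score interval follow from planned outputs. Nothing in the documents points to a primed deficit of 12 to 20 points. With equal vaccines at 90% responders, the row would show at least one lower limit at or below -10% in about 57% of trials, which could itself be over-read. A disclaimer that co-primary 1 is an average over strata would largely repeat what SAP 5.1.1.2.1 already says.

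**Conclusion.** The concern does not hold. It is correct that no listed output gives the primed-only difference in the percentage with hSBA ≥1:8, and that both co-primaries can pass with a primed deficit well above 10 points (19.1 in the example) when the naïve arms are equal. Neither fact is an error. The co-primaries test the two populations they name, secondary objective 3 agrees with its endpoint and method, and no objective claims non-inferiority in primed toddlers alone.

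Followed as written, the plan gives sound conclusions, and its planned exact intervals would expose the severe cases. A descriptive difference for Groups 3 and 4 is a matter of preference: it would sharpen the description, above all at response rates near 90%, but it would alter no test, decision rule or stated conclusion. The size figures rest on assumed response rates, about 10% exclusions and equal naïve arms, one serogroup at a time. All four serogroups must pass.

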5.1.3 Statistical Methods for Observational Objectives

5.1.3.1 Hypotheses

No hypotheses will be tested. Descriptive statistics will be presented.

5.1.3.2 Statistical Methods

Immunogenicity

Descriptive statistics will be provided for the antibody titers against meningococcal serogroups contained in MenACYW conjugate vaccine and Nimenrix[®]. In general, categorical variables will be summarized and presented by frequency counts, percentages, and CIs. The 95% CIs of point estimates will be calculated using the normal approximation for quantitative data and the exact binomial distribution (Clopper-Pearson method) for percentages (1).

For GMTs, 95% CIs of point estimates will be calculated using normal approximation assuming they are log-normally distributed.

Reverse cumulative distribution curve (RCDC) figures will be provided for the antibody titers against meningococcal serogroups contained in MenACYW conjugate vaccine and Nimenrix[®] treatment groups.

In summary, descriptive analyses on A, C, Y, and W serogroups will include but not be limited to:

- hSBA GMT and 95% CI at D0 and D30
- hSBA titer distribution and RCDC
- Percentage of subjects with hSBA titer $\geq 1:4$ and $\geq 1:8$ and 95% CI at D0 and D30
- Percentage of subjects with hSBA titer ≥ 4 -fold rise from pre-vaccination to post-vaccination, and 95% CI

- hSBA vaccine seroresponse¹ rate and 95% CI
- rSBA² GMT and 95% CI at D0 and D30
- rSBA titer distribution and RCDC
- Percentage of subjects with rSBA titer \geq 4-fold rise from pre-vaccination to post-vaccination, and 95% CI
- rSBA vaccine seroresponse³ rate and 95% CI
- Percentage of subjects with rSBA titers \geq 1:8 and \geq 1:128 and 95% CI at D0 and D30

Safety

For this trial, the safety data will be assessed by applying descriptive statistical methods, supplemented by the calculation of CIs to aid interpretation. The exact binomial distribution (Clopper-Pearson method) for proportions will be used in the calculation of the 95% CIs of events.

The frequency and percentage of subjects who had solicited injection site reactions and solicited systemic reactions and their 95% CIs will be provided. These events will be tabulated by the type of reactions and intensity for each study group. These events will also be summarized by other categories specified in the endpoints (e.g. time of onset, number of days of occurrence, actions taken).

Unsolicited AEs will be collected, coded, and summarized by MedDRA system organ class and preferred term. For each unsolicited AE, the number of subjects with at least 1 instance of that event will be reported. Unsolicited AEs will also be tabulated by intensity and relatedness of study vaccine and by other categories specified by the endpoints.

Immediate reactions, SAEs, [REDACTED], and any event that leads to subject withdrawal from the study will be tabulated separately.

Safety tables will be described for subjects who are either meningococcal vaccine naïve or had received monovalent MenC vaccination during infancy (i.e. Group 1 & 3 and Group 2 & 4) and for subjects in all study groups (i.e. based on MenC priming vaccination background).

¹ hSBA vaccine seroresponse is defined as:

- For a subject with a pre-vaccination titer $<$ 1:8, the post-vaccination titer must be \geq 1:16.
 - For a subject with a pre-vaccination titer \geq 1:8, the post-vaccination titer must be at least 4-fold greater than the pre-vaccination titer.
- ² In a subset of subjects per group: 100 subjects each in Group 1 and Group 2; 50 subjects in each subgroup (MenC-TT or MenC-CRM primed subjects) in Group 3; 25 subjects in each subgroup (MenC-TT or MenC-CRM primed subjects) in Group 4
- ³ rSBA vaccine seroresponse is defined as a post-vaccination titer \geq 1:32 for subjects with pre-vaccination rSBA titer $<$ 1:8, or a post-vaccination titer \geq 4 times the pre-vaccination titer for subjects with pre-vaccination rSBA titer \geq 1:8.

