--	--

	
Observational Objectives
 
Immunogenicity
 
Descriptive statistics will be provided for the antibody titers against meningococcal serogroups contained in MenACYW conjugate vaccine and Nimenrix®. In general, categorical variables will be summarized and presented by frequency counts, percentages, and CIs. The 95% CIs of point estimates will be calculated using the normal approximation for quantitative data and the exact binomial distribution (Clopper-Pearson method) for percentages. For GMTs, 95% CIs of point estimates will be calculated using normal approximation assuming they are log-normally distributed.
 
Reverse cumulative distribution curve (RCDC) figures will be provided for the antibody titers against meningococcal serogroups contained in MenACYW conjugate vaccine and Nimenrix® treatment groups.
 
In summary, descriptive analyses on A, C, Y, and W serogroups will include but not be limited to:
 
 
• hSBA GMT and 95% CI at D0 and D30
 
• hSBA titer distribution and RCDC
 
• Percentage of subjects with hSBA titer <math>\geq 1:4</math> and <math>\geq 1:8</math> and 95% CI at D0 and D30
 
• Percentage of subjects with hSBA titer <math>\geq 4</math>-fold rise from pre-vaccination to post-vaccination, and 95% CI
 
• hSBA vaccine seroresponse* rate and 95% CI
 
• rSBA† GMT and 95% CI at D0 and D30
 
• rSBA† titer distribution and RCDC
 
• Percentage of subjects with rSBA† titer <math>\geq 4</math>-fold rise from pre-vaccination to post-vaccination, and 95% CI
 
• rSBA† vaccine seroresponse‡ rate and 95% CI
 
• Percentage of subjects with rSBA† titer <math>\geq 1:8</math> and <math>\geq 1:128</math> and 95% CI at D0 and D30
 
 
*hSBA vaccine seroresponse for serogroups A, C, Y, and W is defined as:
 
 
• For a subject with a pre-vaccination titer <math>< 1:8</math>, the post-vaccination titer must be <math>\geq 1:16</math>.
 
• For a subject with a pre-vaccination titer <math>\geq 1:8</math>, the post-vaccination titer must be at least 4-fold greater than the pre-vaccination titer.
 
 
† in a subset of subjects per group: 100 subjects each in Group 1 and Group 2; 50 subjects in each subgroup in Group 3 (MenCC-TT or MenC-CRM primed subjects); 25 subjects in each subgroup in Group 4 (MenC-TT or MenC-CRM primed subjects)
 
‡rSBA vaccine seroresponse is defined as a post-vaccination rSBA titer <math>\geq 1:32</math> for subjects with pre-vaccination rSBA titer <math>< 1:8</math>, or a post-vaccination titer <math>\geq 4</math> times the pre-vaccination titer for subjects with pre-vaccination rSBA titer <math>\geq 1:8</math>.
 
Safety
 
Safety results will be described for subjects in each study groups. The main parameters for the safety endpoints will be described by 95% CIs (based on the Clopper-Pearson method).

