3.1 Trial Design

This was a Phase III, modified double-blind, randomized, parallel-group, active-controlled, multi-center trial to compare the immunogenicity and describe the safety of a single dose of MenACYW conjugate vaccine to a single dose of a licensed quadrivalent meningococcal polysaccharide groups A, C, W-135, and Y conjugate vaccine, Nimenrix[®], in toddlers (12 to 23 months of age) in the EU who are either meningococcal vaccine naïve or received monovalent MenC vaccination during infancy.

Approximately 918 healthy toddlers aged 12 to 23 months were to be enrolled and randomized as follows depending on the meningococcal background:

Meningococcal Vaccine-Naïve Subjects: 612 subjects were to be randomized in a 1:1 ratio to the following 2 groups:

- Group 1: MenACYW conjugate vaccine (n=306)
- Group 2: Nimenrix[®] (n=306)

MenC-Primed Subjects: 306 subjects were to be randomized in a 2:1 ratio to the following 2 groups:

- Group 3: MenACYW conjugate vaccine (n=204)
- Group 4: Nimenrix[®] (n=102)

Enrollment of MenC-primed subjects was stratified by the type of primed vaccine, MenC-TT (NeisVac-C[®]) or MenC-CRM (Menjugate[®], Meningitec[®]), considering that at least 25% and a maximum of 50% of subjects had been primed with MenC-CRM as described in Table 3.1 below:

Table 3.1: MenC priming strategy

Priming	Group 3 MenACYW conjugate vaccine	Group 4 Nimenrix [®]
MenC-TT	102 - 152*	51 - 76*
MenC-CRM	52* - 102	26* - 51

Total	204	102
--------------	-----	-----

*Sample size corresponding to 25% of subjects primed with MenC-CRM

All subjects were to provide blood samples for immunogenicity assessment at baseline (pre-vaccination) and at 30 to 44 days post-vaccination.

Solicited adverse event (AE) information were to be collected for 7 days after vaccination, unsolicited AE information were to be collected from Visit (V) 01 (Day [D] 0) to V02 (D30 [+14 days]), and serious adverse event (SAE) information, [REDACTED] were to be collected throughout the trial.

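### Do the pooled safety columns mislead because 40% of one and 25% of the other are MenC-primed?

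*SAP*

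**What the plan says.** SAP 3.1 gives the trial separate purposes for the two kinds of data: to "compare the immunogenicity and describe the safety of a single dose of MenACYW conjugate vaccine" against Nimenrix. Allocation differs by priming status. For naïve toddlers, "612 subjects were to be randomized in a 1:1 ratio to the following 2 groups" (306 and 306). For MenC-primed toddlers, "306 subjects were to be randomized in a 2:1 ratio to the following 2 groups" (204 and 102).

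The safety part of SAP 5.1.3.2 lays out its tables as "i.e. Group 1 & 3 and Group 2 & 4) and for subjects in all study groups (i.e. based on MenC priming vaccination background". That means two pooled columns by vaccine, plus the four randomized groups. For solicited reactions the same section adds: "These events will be tabulated by the type of reactions and intensity for each study group". The Protocol Synopsis agrees: "Safety results will be described for subjects in each study groups". On intervals, SAP 5.1.3.2 says: "The exact binomial distribution (Clopper-Pearson method) for proportions will be used in the calculation of the 95% CIs of events". These are intervals for single proportions.

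On inference for all observational objectives, safety included, SAP 5.1.3.1 says: "No hypotheses will be tested. Descriptive statistics will be presented". Protocol 9.1.2 and 9.2.2 state that safety has neither a primary nor a secondary objective.

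**The concern.** The pooled columns look like the overall comparison of the two vaccines, and they are the only display that puts all subjects into one column per vaccine. Yet their composition differs by design. The 2:1 allocation in the primed stratum puts proportionally more primed toddlers into the MenACYW column, and good randomization does not remove that.

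The SAP takes account of this elsewhere. The pooled response rates (SAP 5.1.1.2.1) and the pooled titer ratio (SAP 5.1.2.2.1) are both stratified on priming status. The pooled safety columns carry neither a stratified contrast nor a written caution. Protocol 1.1, Protocol 1.4 and SAP 1 also use comparative language about safety.

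At stake would be a spurious safety difference. If primed toddlers react more often, MenACYW would look worse than it is. If they react less often, it would look better.

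**Working it through.** **Inputs.** Group sizes and ratios come from SAP 3.1. All event rates below are assumptions, because the documents give none by priming status.

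**The plan's own sizes.** 612 × 1/2 = 306 and 306. 306 × 2/3 = 204, and 306 × 1/3 = 102. The total is 306 + 306 + 204 + 102 = 918, as stated.

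**Priming mix.**
- Groups 1 and 3: 204/(306 + 204) = 204/510 = 40%.
- Groups 2 and 4: 102/(306 + 102) = 102/408 = 25%.
- With an assumed loss of up to 10% in either stratum, the shares move to 37.5–42.6% and 23.1–27.0%, so the imbalance stays.

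**Artefact in a crude subtraction.** With no vaccine effect in either stratum, the pooled difference is (0.40 − 0.25) × (primed rate − naïve rate) = 0.15 × gap.

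| Assumed gap (points) | Artefact (points) |
|---|---|
| 0 | 0 |
| 5 | 0.75 |
| 10 | 1.5 |
| 20 | 3.0 |
| −10 | −1.5 |

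For scale, at a 40% rate in every group the standard error of the crude pooled difference is √[0.24 × (1/510 + 1/408)] = 3.25 points. Gaps of 5 to 10 points therefore give roughly a quarter to a half of a standard error.

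**What would follow if a reader formed an interval.** In simulation (400,000 trials per case, identical vaccines, naïve rate 40%), a crude 95% score interval for the pooled difference excludes zero in 5.6%, 7.3% and 14.3% of trials at gaps of 5, 10 and 20 points. A priming-stratified interval stays at about 5%. The crude figures describe an interval that the SAP does not plan.

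**What the planned tables would show.** Take naïve 30%, primed 50% and identical vaccines:
- Pooled MenACYW: (306 × 0.30 + 204 × 0.50)/510 = 193.8/510 = 38%.
- Pooled Nimenrix: (306 × 0.30 + 102 × 0.50)/408 = 142.8/408 = 35%.
- Group 1 and Group 2: 30% and 30%.
- Group 3 and Group 4: 50% and 50%.

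The pooled percentages correctly state what happened in each column. The by-group columns show that the 3-point gap is mix and not vaccine. Their denominators (306, 306, 204, 102) disclose the mix, and their counts let a reader compute a stratified difference.

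**Consistency with the immunogenicity analyses.**
- SAP 5.1.1.2.1 and 5.1.2.2.1 estimate a pooled difference and a pooled ratio between vaccines, and both are stratified.
- Observational immunogenicity in SAP 5.1.3.2, the same tier as safety, is reported as single percentages with Clopper-Pearson intervals and single geometric means, with no stratified contrast.

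Stratification thus follows the estimand: it is used where a pooled contrast is estimated. Safety has no such contrast to stratify.

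**The case for a change.** The strongest case for acting has three parts.

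First, a comparative reading is foreseeable. Protocol 1.1 states an aim of showing comparable safety profiles, and the pooled columns appear only in the SAP, having no counterpart in the protocol's safety text. This stands as a caution to the reader. The introductory prose specifies no analysis, however, and the operative safety objective (Protocol 2.3, SAP 2.3) is to evaluate each vaccine's profile. The pooled layout is additional to the by-group tables and does not replace them.

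Second, the within-stratum comparisons are less precise than a stratified difference over both strata. At 40% rates the 95% half-widths are 7.75 points for Group 1 against 2 and 11.57 for Group 3 against 4, compared with 6.45 for a Mantel-Haenszel-weighted difference with a score interval. This is true, but it matters only if a between-vaccine difference is to be estimated, and no stated objective asks for one.

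Third, a stratified risk difference for a few common endpoints would cost little. Against that, the endpoints, weights and interval method would all have to be newly chosen. Five unplanned intervals would have a 1 − 0.95⁵ = 23% chance that at least one excludes zero under identical vaccines, if they were independent. That invites the over-reading it is meant to prevent. Statisticians may reasonably differ on whether to add it, so it is a matter of preference.

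A footnote giving the priming mix would do no harm, but it would only repeat what the four-group denominators already show. Table shells are not among the documents, so the absence of such a note cannot be established.

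**Conclusion.** The concern does not hold. The imbalance is real (40% against 25% primed at planned sizes), and its possible effect on a crude subtraction is 0.15 times the primed-minus-naïve rate gap: 0.75 to 3.0 points for assumed gaps of 5 to 20 points, and zero if the rates are equal. No planned output makes that subtraction. Each pooled percentage and its exact interval correctly describes its own column, and the unconfounded comparisons are planned alongside. Followed as written, the safety analysis gives sound descriptive results.

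This rests on two conditions: that the by-group tables are produced as SAP 5.1.3.2 and the Protocol Synopsis say, and that safety stays descriptive. If the study report were to draw a between-vaccine safety conclusion, it should rest on Group 1 against 2 and Group 3 against 4, not on the pooled columns.
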